5.3 Follow-Up

“Data were collected at three time points: baseline, 3 months, and 6 months. Caregivers completed all surveys on behalf of the person with memory loss. Participants were asked for their opinion of their relative with memory loss (eg “How often does your relative feel confident?”). At baseline, surveys for participants caring for a person with memory loss measured ADLs, memory impairment, memory and problem behaviors, social interaction, and quality of life as well as demographic questions asking about themselves and the person with memory loss. Participants with memory loss who did not have a caregiver completed surveys on their own behalf. They received a slightly different version of the survey with questions being asked in reference to themselves (eg, “How often do you feel confident?”). Their baseline survey measured ADLs, memory impairment, social interaction, and quality of life as well as demographic questions about themselves. Surveys administered at 3 and 6 months were identical to the baseline surveys except that they did not include demographic questions. At 3 and 6 months, participants in the intervention group completed an additional feasibility and utility checklist. Participants were given the option to complete an online or paper version of the surveys.” (see <https://www.ncbi.nlm.nih.gov/pmc/articles/PMC6715400/>)

SOCIAL PROTOCOL (HRP-580)**PROTOCOL TITLE:** Social Support Aid for People with Dementia**VERSION DATE:** 5/8/2017**5.4 Individually Identifiable Health Information**

Survey data per above were relied upon.

6.0 Data Banking

n/a

7.0 Sharing of Results with Participants

7.1 Upon publication of the peer-reviewed manuscript summarizing the findings (see <https://www.ncbi.nlm.nih.gov/pmc/articles/PMC6715400/>; note that the publication is open access), the manuscript was emailed to all participants.

8.0 Study Duration

8.1 Individuals participated in the study for up to 6 months. Participants were enrolled over a roughly 12 month period. All study procedures were completed in roughly 24 months.

9.0 Study Population

9.1 Inclusion Criteria: PWMCs must be: diagnosed by a physician with early-stage Alzheimer's disease, mild cognitive impairment, or a self-identified concern of memory loss; able to complete surveys in English or Spanish; SLUMS score of 20 or above. Care partners of PWMCs must be: 21 years of age and over; self-identify as someone who provides assistance to the PWMC because of their memory loss (these individuals are called "care partners," as these individuals may or may not provide the intensive hands-on care typical of "caregivers"); and indicate a willingness to use the SSA

9.2 Exclusion Criteria: Those who were not willing to utilize SSA.

9.3 Screening: A research assistant screened potential participants over the telephone or via an online form to determine eligibility.

10.0 Vulnerable Populations**10.1 Vulnerable Populations:**

Population / Group	Identify whether any of the following populations will be primary focus of the research (targeted), included but not the focus of the research or excluded from participation in the study.
Children	Choose an item.

SOCIAL PROTOCOL (HRP-580)**PROTOCOL TITLE:** Social Support Aid for People with Dementia**VERSION DATE:** 5/8/2017

Pregnant women/fetuses/neonates	Choose an item.
Prisoners	Choose an item.
Adults lacking capacity to consent and/or adults with diminished capacity to consent, including, but not limited to, those with acute medical conditions, psychiatric disorders, neurologic disorders, developmental disorders, and behavioral disorders	Primary focus of the research
Non-English speakers	Choose an item.
Those unable to read (illiterate)	Choose an item.
Employees of the researcher	Choose an item.
Students of the researcher	Choose an item.
Undervalued or disenfranchised social group	Choose an item.
Active members of the military (service members), DoD personnel (including civilian employees)	Choose an item.
Individual or group that is approached for participation in research during a stressful situation such as emergency room setting, childbirth (labor), etc.	Choose an item.
Individual or group that is disadvantaged in the distribution of social goods and services such as income, housing, or healthcare.	Choose an item.

SOCIAL PROTOCOL (HRP-580)**PROTOCOL TITLE:** Social Support Aid for People with Dementia**VERSION DATE:** 5/8/2017

Individual or group with a serious health condition for which there are no satisfactory standard treatments.	Choose an item.
Individual or group with a fear of negative consequences for not participating in the research (e.g. institutionalization, deportation, disclosure of stigmatizing behavior).	Choose an item.
Any other circumstance/dynamic that could increase vulnerability to coercion or exploitation that might influence consent to research or decision to continue in research.	Choose an item.

10.2 Additional Safeguards:

The experience of the University of Minnesota research team will minimize the possibility of psychological risks. The unlikelihood of such problems is evident from the absence of any clinically significant problems during the past eight years that [name] has operated various protocols related to dementia caregiving research. The RA will be trained to interview in ways that are non-threatening, friendly, and respectful. We will emphasize to all participants that they do not have to complete any question they do not want to answer, and that the interview may be terminated at any time according to their wishes. We will stress to care partners or PWMCS that their decision to discontinue the study will in no way affect the services they are receiving from the University of Minnesota or other entities.

In the event a care partners or PWMCS does become upset during the interview process, the RA will contact [name] who will be available for consultation. If a participant is in crisis because of their care situation or some other reason, research staff will be instructed to consult with [name]. With the participant's permission, we will then contact the appropriate resource person in an external agency (e.g., the Alzheimer's Association). Based on the research team's experience working with caregiving families, we expect no or very few such instances to occur. If a member of the research team does identify neglect or other potentially inappropriate care practices, the state Ombudsman will be notified to protect the rights of persons with dementia and their families.

SOCIAL PROTOCOL (HRP-580)

PROTOCOL TITLE: Social Support Aid for People with Dementia

VERSION DATE: 5/8/2017

10.3 If research includes potential for direct benefit to participant, provide rationale for any exclusions indicated in the table above:

We believed participation in the SSA evaluation would yield benefits for participants. We hypothesized that the SSA would provide PWMCs with greater opportunity for social engagement and thus enhanced quality of life.

11.0 Number of Participants

11.1 Number of Participants to be Consented: 48 participants consented for this study

12.0 Recruitment Methods

12.1 Individuals with dementia, memory loss, or memory concerns, as well as their caregivers, were recruited from the University of Minnesota Caregiver Registry (a registry of caregivers who gave permission to be contacted about opportunities to participate in research), the Minnesota State Fair, and through statewide newspaper advertisements from February to October 2017.

12.2 Recruitment Materials: Email and telephone scripts as well as flyers were used to recruit potential participants.

12.3 Payment: Participants were offered \$100 upon completion of the 6-month follow-up surveys/interviews.

13.0 Withdrawal of Participants

Per <https://www.ncbi.nlm.nih.gov/pmc/articles/PMC6715400/>: "A total of 58 potential participants were assessed for eligibility; of these, all but one met the inclusion criteria. Six of the 58 potential participants were unwilling to provide informed consent and were not included in the study. None of the participants expressed unwillingness to be randomized. Of the 48 participants that were randomized, 44 finished the study (92% retention rate). Two participants with memory loss refused participation after undergoing randomization to the intervention group. Two participants who were caregivers were lost to follow-up, both in the intervention group."

14.0 Risks to Participants

The study had several risks: since the study involved no invasive procedures, we did not anticipate any physical risks to the family member or clients. It was possible, although did not occur, when participants could have become upset with questions or thinking about the person with memory loss or their situations. The potential social or legal risks for participants only related to possible violations of confidentiality which again did not occur. Given our data security procedures, we believed such risks were highly unlikely (we would estimate the likelihood of these risks at 5% or under).

15.0 Incomplete Disclosure or Deception

Not applicable

SOCIAL PROTOCOL (HRP-580)

PROTOCOL TITLE: Social Support Aid for People with Dementia

VERSION DATE: 5/8/2017

16.0 Potential Benefits to Participants

16.1 Potential Benefits: There were no direct benefits to participants that were anticipated.

17.0 Statistical Considerations

17.1 Data Analysis Plan From:

<https://www.ncbi.nlm.nih.gov/pmc/articles/PMC6715400/>.

“Recruitment, Randomization, and Retention

Chi-square and t tests were used to determine if participant demographics in the intervention and control groups were significantly different ($P<.05$). Chi-square and t tests were also used to compare participants who were lost to follow-up with those who were not.

Feasibility and Utility

Participants in the intervention group were asked to complete an additional survey at 3 and 6 months to assess their perceptions of feasibility and utility. This checklist included 15 Likert scale items asking participants to rate their level of agreement with statements such as “the technology works well,” “SSA was easy to use,” and “my relative felt lost using SSA” ($\alpha=.89$).

Assessment of Intervention Effect

Descriptive statistics were calculated for measures of quality of social interaction and quality of life. Social interaction quality was measured by asking participants to rate their satisfaction with the following types of communication: visits, phone calls, mail correspondence, and computer correspondence. Quality of life was measured using the Pleasant Events Schedule-Alzheimer’s Disease (PES-AD; frequency $\alpha=.84$; enjoyment $\alpha=.76$) and Dementia Quality of Life (DQoL; $\alpha=.92$). The PES-AD asks with what frequency and level of enjoyment the person with memory loss experiences a list of pleasant activities (eg, being outside, listening to music, laughing). The DQoL asks participants to use a Likert scale to rate how often the person with memory loss feels a certain way (eg, satisfied, cheerful, angry, worried).

We imputed missing data using a Markov chain Monte Carlo method to conduct a five-fold multiple imputation. Analyses were conducted as intention to treat. Change scores were calculated to determine differences between outcomes at baseline and 6 months. To determine whether changes in satisfaction and quality of life in the intervention group were significantly different than changes in the control group, t tests were used. Statistical significance was assessed using two-tailed tests with a significance level of $P=.05$.

SOCIAL PROTOCOL (HRP-580)

PROTOCOL TITLE: Social Support Aid for People with Dementia

VERSION DATE: 5/8/2017

Qualitative Analysis

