5.0 Procedures Involved

5.1 Study Design:

A parallel randomized controlled pilot trial design.

5.2 Study Procedures:

“Following completion of the baseline survey, participants were randomly assigned to either receive the technology or to continue with usual care. Participants were randomized at a ratio of 1:1 using a random number generator. Neither the participants nor researchers were blinded to randomization group. Research assistants met with participants in the intervention group in-person to provide the mobile phone and smartwatch and demonstrate how to use the SSA technology. Participants were given the technology to use at their discretion, and there was no requirement for how many times they had to use the SSA. Throughout the study, research assistants and the SSA developer provided technical support and answered questions regarding the technology. Participants in the control group were given the technology free of charge after completing the study.” (see <https://www.ncbi.nlm.nih.gov/pmc/articles/PMC6715400/>)

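### Baseline comparability is assessed only by P<.05 tests on demographics, which at about 24 per arm cannot flag an observed difference below about 0.58 SD, and no adjusted effect estimate is planned

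*Combined protocol and SAP*

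**What the plan says.** Allocation followed the baseline survey. Section 5.2 states: "Participants were randomized at a ratio of 1:1 using a random number generator". It mentions no blocking or stratification. Section 13.0 gives the number: "Of the 48 participants that were randomized, 44 finished the study (92% retention rate"). Arm sizes are not given.

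The only between-arm baseline comparison described is in Section 17.1, under recruitment, randomization and retention: "Chi-square and t tests were used to determine if participant demographics in the intervention and control groups were significantly different", with P<.05 as the criterion.

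Section 5.3 lists the other baseline measures separately from the demographic questions. The caregiver version "measured ADLs, memory impairment, memory and problem behaviors, social interaction, and quality of life as well as demographic questions". For people with memory loss who answered for themselves: "Their baseline survey measured ADLs, memory impairment, social interaction, and quality of life as well as demographic questions about themselves". ADL and memory impairment are therefore in both versions; problem behaviours are in the caregiver version only.

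For the effect, Section 17.1 says: "Change scores were calculated to determine differences between outcomes at baseline and 6 months". The arms are compared on these changes by t test, and no covariate is named. The same section says descriptive statistics were calculated for social interaction quality and quality of life, without saying at which visit or whether by arm. Section 17.2 gives no power analysis.

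**The concern.** When a random number generator forms the arms, every baseline difference arises by chance. The hypothesis under test is already known to be true, so the P value does not answer the useful question: is there an imbalance large enough, in a variable prognostic enough, to matter for the effect estimate? In a trial of 48, large differences can easily be non-significant.

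The tests also look at demographics, whereas function, cognition and the baseline outcome scores are more likely to predict change over 6 months. The population is mixed (early-stage Alzheimer's disease, mild cognitive impairment or self-identified memory concern, Section 9.1), so a chance imbalance in those scores is plausible.

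At stake is how the SSA effect is read. The single planned estimate is unadjusted, and nothing else in the plan would show a reader whether a chance imbalance had helped to create or hide a difference.

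**Working it through.** The documents state no power or sample-size figure, so there is none to reproduce.

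**Inputs**
- Level 0.05 (Section 17.1). Two-sided testing is stated for the effect analysis ("Statistical significance was assessed using two-tailed tests with a significance level of $P=.05") and assumed here for the baseline t tests.
- 48 randomised (Section 13.0), ratio 1:1 (Section 5.2). 24 per arm is an assumption; splits down to 16/32 were checked.
- The correlation of a baseline score with change is not in the documents. It is assumed to be 0.3 to 0.5.

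**1. Smallest observed difference that is flagged.** With t = d / sqrt(1/n1 + 1/n2) on 46 df, the cut-off is d = 2.013 × sqrt(1/24 + 1/24) = 2.013 × 0.2887 = 0.58 pooled SD. At 16/32 it is 2.013 × 0.3062 = 0.62 SD.

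**2. An observed 0.5 SD difference.** t = 0.5 / 0.2887 = 1.73, p = 0.090. It passes every time at 24/24, and also at 16/32 (p = 0.109).

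**3. A binary variable.** For 12/24 against 18/24 (50% v 75%), the uncorrected chi-square gives p = 0.074, or p = 0.136 with continuity correction. This passes too.

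**4. How often such imbalance arises under random allocation.** For any one continuous variable, an observed difference above 0.3 SD corresponds to |t| > 0.3 / 0.2887 = 1.04, which has probability 0.304. The test flags 0.05 by construction, so (0.304 − 0.05) / 0.304 = 84% of these go unflagged. A difference of 0.5 SD or more occurs in about 8–9% of simulated 24/24 splits, and 42–44% of those pass.

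**5. Why the change score does not remove the imbalance.** If the SDs at baseline and 6 months are equal and the two visits correlate at r, baseline correlates with change at −sqrt((1 − r)/2). At r = 0.82 this is −sqrt(0.09) = −0.3; at r = 0.5 it is −sqrt(0.25) = −0.5. Regression to the mean alone thus gives the assumed 0.3 to 0.5 for the baseline outcome score.

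**6. Largest shift from an unflagged imbalance.** Imbalance × correlation: 0.581 × 0.3 = 0.17 and 0.581 × 0.5 = 0.29 SD of the change score. The standard error of the unadjusted difference is 1 × sqrt(2/24) = 0.29 SD on the same scale.

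**7. What adjustment buys.** Adjusting for a covariate correlated 0.3 to 0.5 with change multiplies the residual variance by 1 − 0.3² = 0.91 to 1 − 0.5² = 0.75, a reduction of 9% to 25%. Three covariates take the residual degrees of freedom from 46 to 43.

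**The case against.** The strongest reply is that the tests feed nothing. Section 17.1 attaches no covariate choice, no adjustment rule and no statement of comparability to them, so deleting them leaves every SSA estimate, interval and P value unchanged. The unadjusted t test is valid under randomisation: its standard error already allows for chance imbalance, and the worst unflagged shift in step 6 is no larger than one standard error. All of this stands. It limits the point to how baseline is reported and to the missing adjusted estimate.

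A second reply is that baseline scores are not ignored, because they enter through the change score and may be among the descriptive statistics. That is fair for the outcomes, but step 5 shows that a change score leaves part of an imbalance in place, and the descriptive statement does not mention ADL or memory impairment. Section 17.1 is an excerpt from a publication, and these documents do not show what was tabulated there.

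Three stronger readings are tempting and are not supported:
- That the plan decides comparability by these tests, or will present non-significance as proof of balance. The text says neither.
- That the tests miss a 0.5 SD imbalance about six times in ten. That figure (60.4% at 24 per arm) is the type II error rate for a true population shift, which random allocation excludes. For a realised imbalance of 0.5 SD, the test never flags it.
- That some given chance of a false flag across all demographics can be quoted. The documents do not say how many were tested.

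**Conclusion.** The point holds as one of reporting and of precision. Section 17.1 relies on baseline significance tests that cannot show balance, applies them as written to the less informative variables, and offers only an unadjusted effect estimate. An observed difference of up to about 0.58 SD in a continuous variable goes unflagged at 24 per arm (0.62 SD at 16/32). If such an imbalance lay in a score correlated 0.3 to 0.5 with change, the estimate would move by 0.17 to 0.29 SD of change.

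This rests on the assumed arm sizes and correlations, and on two-sided baseline tests. The insensitivity does not depend on the exact split. A reader might go on to infer that the planned comparison is invalid or that the arms were in fact unbalanced; the documents show neither.

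**What to change.** Replace the between-arm baseline P values with a by-arm table, with standardised differences, of demographics, ADL, memory impairment and the baseline outcome scores (DQoL, Cantril ladder, satisfaction with social interaction). Include PES-AD only if it was collected at baseline. Section 3.2 gives its time frame as 3 and 6 months, while Section 5.3 says the follow-up surveys matched baseline apart from demographics, and this should be reconciled.

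Whatever that table shows, report beside the change-score t test a 6-month comparison of the arms adjusted for the baseline value of that outcome, ADL and memory impairment, with estimate and interval. Keep this covariate set fixed across outcomes. Section 26.1 says the study is complete, so label the analysis post hoc.

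The cost is three residual degrees of freedom, one additional analysis and one table from baseline data that Section 5.3 says were collected. The report also gives up any statement that the groups did not differ significantly at baseline.

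### With only five imputations, a result near P=.05 could change verdict from one imputation run to the next; clear results are not affected (minor)

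*Combined protocol and SAP*

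**What the plan says.** Section 17.1 (Assessment of Intervention Effect) describes the handling of missing data in one sentence: "We imputed missing data using a Markov chain Monte Carlo method to conduct a five-fold multiple imputation". The outcome is the baseline-to-6-month change: "Change scores were calculated to determine differences between outcomes at baseline and 6 months". The arms are compared by t test, and the decision rule follows: "Statistical significance was assessed using two-tailed tests with a significance level of" .05. The section gives no seed, imputation model, pooling rule, Monte Carlo error or reason for choosing five.

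On the amount of missing data, section 13.0 reports: "Of the 48 participants that were randomized, 44 finished the study (92% retention rate"). Two of the four losses were refusals: "Two participants with memory loss refused participation after undergoing randomization to the intervention group". The other two were caregivers lost to follow-up, also in the intervention arm. Sections 10.2 and 20.2 let any participant skip any question, so item non-response may add to this in either arm. Its amount is not given. Section 17.2 gives no power analysis.

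**The concern.** Multiple imputation draws the missing values at random, so the pooled estimate, its standard error and the P value vary from run to run. The usual defence of five imputations is that the variance of the estimate is barely inflated when little is missing. That is a statement about efficiency. A yes/no rule at .05 also needs the P value to be stable to within the distance between the result and the threshold. If it is not, two analysts who follow 17.1 exactly can report opposite verdicts from the same data. What is at stake is the reproducibility of a near-threshold result.

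**Working it through.** **Inputs from the documents.** 48 randomized and 44 finished (13.0); m = 5 and two-sided .05 (17.1); t test on baseline-to-6-month change (17.1); 1:1 allocation (5.2). The plan's own figure reproduces: 44/48 = 91.7%, which rounds to 92%. Four of 48 is 8.3% missing.

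**Assumptions.** 24 per arm (arm sizes are not given), normal scores, and 6-month scores imputed from arm and baseline. The baseline-to-6-month correlation ρ is taken as 0.5 to 0.7, with 0.3 to 0.85 as a wider range.

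**Step 1: missing information.** With unit variances and 4 of 24 missing in one arm:

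- Between-imputation variance: B ≈ (4/24)² × (1 − ρ²) × (1/20 + 1/4) = 0.00833(1 − ρ²).
- Complete-data variance of the difference in mean change: W = 2(1 − ρ) × (1/24 + 1/24) = 0.1667(1 − ρ).
- Ratio: B/W = 0.05(1 + ρ), which is 0.075 at ρ = 0.5 and 0.085 at ρ = 0.7.
- Fraction of missing information: 0.075/1.075 = 7.0% and 0.085/1.085 = 7.8%.
- With the factor 1 + 1/m at m = 5: 0.090/1.090 = 8.3% and 0.102/1.102 = 9.3%.

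Simulation gave 6.6 to 9.3% over ρ = 0.3 to 0.85. About 7 to 10% covers all of these.

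**Step 2: approximate switching probability.** The run-to-run SD of the pooled z is about √(FMI/m). With FMI = 0.08 and m = 5 this is √0.016 = 0.126. The probability of landing on the other side of .05 is 1 − Φ(|z_P − 1.960|/SD).

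- Stable P = .04: (2.054 − 1.960)/0.126 = 0.74, giving 23%.
- Stable P = .06: (1.960 − 1.881)/0.126 = 0.63, giving 27%.
- With m = 50 the SD is √0.0016 = 0.040. The same two cases give about 1% and 2%.

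**Step 3: simulation.** This also carries the run-to-run variation in the pooled standard error and degrees of freedom. It used 24 v 24, Bayesian normal imputation, Rubin pooling with Barnard-Rubin degrees of freedom, and 60 data sets with 1,500 reruns each. Every data set was shifted to a set stable P. The table gives the share of reruns on the other side of .05 with the four documented losses, over ρ = 0.3 to 0.85.

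| Stable P | m=5 | m=20 | m=50 | m=100 |
|---|---|---|---|---|
| .03 | 7–13% | <1% | 0% | 0% |
| .04 | 26–31% | 7–12% | 1–3% | <1% |
| .045 | 39–42% | 24–29% | 13–18% | 6–10% |
| .05 | about half | about half | about half | about half |
| .055 | 34–36% | 23–28% | 13–18% | 6–10% |
| .06 | 23–27% | 8–13% | 2–4% | <1% |
| .07 | 9–14% | 1–2% | 0% | 0% |

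At m = 5 the SD of the P value across reruns was 0.016 to 0.021 when the stable P was .05.

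**Step 4: sensitivity to item non-response (assumed amounts, ρ = 0.5 to 0.7).** With 8 missing (6 and 2 by arm), m = 5 gives 38–40% at .04 and 30–31% at .06; m = 50 gives 7–9% and 9–10%. With 12 missing (8 and 4), m = 5 gives 43–45% and 32–33%; m = 50 gives 14–16% and 14–15%.

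**Step 5: all possible results, not only near-threshold ones.** Under the null, the chance that two reruns disagree is about (2/√π) × SD × density of |z| at 1.96 = 1.128 × 0.13 × 0.117 = 1.7%, or about 2%.

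**The case against.** The strongest reply is that the large percentages apply only to results already near the threshold. This stands. For stable P between .035 and .049, about a third of reruns at m = 5 cross .05, and a reader might infer that the trial's verdict as such hangs on the seed. The documents do not support that. They report no P value, so nothing shows that any result was borderline, and the overall null figure is about 2% per test. Section 17.1 does name seven scores: satisfaction with four types of communication, two PES-AD scales and DQoL. If all were tested and were independent (both assumptions), the chance of at least one disagreement would be 1 − (1 − 0.017)⁷ ≈ 11%. That is not negligible, but it is far from a third per result.

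A reader might also infer that losses confined to the intervention arm make the seed problem worse. They do not: Monte Carlo error in either arm's mean enters the difference in the same way. One-arm loss raises a question of bias, which no number of imputations answers. Nor are all missing values known to lie in that arm, since any participant could skip items.

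Two further replies stand in part. More imputations do not rescue a result at exactly .05, which is a limit of any hard threshold. The 3-month scores, if used in the imputation model, could lower the missing information for anyone who supplied them, so the figures above may be somewhat high on that count.

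Finally, this is a pilot without a power analysis, and the documents tie no confirmatory decision to the P value. That limits the weight of the point. It does not make five imputations preferable to fifty.

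**Conclusion.** The point holds as a minor one. Under 17.1, a result with stable P between about .04 and .06 would change verdict in roughly 25 to 50% of reruns at m = 5. This rests on the four documented losses, an assumed 24 per arm, normal scores and a correlation of 0.5 to 0.7. Outside that band the effect fades quickly, to about 10% at .03 or .07, and clear results are safe. The shares would be higher if item non-response added to the missing data, but the documents do not say how much there was. None of this shows that a reported finding is wrong.

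**What to change.** Rerun the imputation with at least 50 imputations and a recorded seed. Report the Monte Carlo error of the pooled difference, √(B/m), with each result. A seed alone makes one run repeatable but leaves the verdict just as arbitrary, so m must rise as well. With the documented losses, m = 50 cuts switching to about 1 to 4% at a stable P of .04 or .06. If item non-response proves substantial, let the Monte Carlo error decide whether 50 is enough.

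Section 17.1 reports a completed analysis, so changing the number alone would misdescribe what was done. Revise it after the rerun, and name the variables in the imputation model at the same time.

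The cost is a short computing run and a few sentences. No new data are needed. Sections 18.9 to 18.12 indicate that de-identified data sets exist and that no disposal is planned. Baseline surveys preceded randomization (5.2), so baseline scores should exist for the four losses. Bias from one-arm dropout needs separate treatment.

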3.0 Study Endpoints/Events/Outcomes

- 3.1 Primary Endpoint/Event/Outcome:

Change in Dementia Quality of Life [Time Frame: Baseline, 3-months, and 6-months]

The 21-item modified Dementia Quality of Life instrument is a self-report survey that assesses various domains of quality of life in the person with dementia.

Change in Cantril quality of life ladder [Time Frame: Baseline, 3-months, and 6-months]

The Cantril quality of life ladder is a single item survey that asks respondents to rate their overall quality of life on a scale of 0 (bottom of the latter) to 10 (top of the ladder).

- 3.2 Secondary Endpoint(s)/Event(s)/Outcome(s):

Pleasant events and activities of person with memory concerns [Time Frame: 3-months and 6-months]

The Pleasant Events and Activities-AD Schedule Short Form is a 17-item self-report survey that measures the degree of enjoyment persons with dementia have engaging in a range of activities.

Change in the frequency and quality of social interactions of persons with memory concerns [Time Frame: Baseline, 3-months, and 6-months]

Series of weekly, self-report calendar measures on types and quality of social interactions, developed for this study.

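### The DQoL arm comparison is a t test on change with no baseline adjustment: valid, but less precise than ANCOVA unless the baseline slope is near 1 (with equal SDs, a correlation above about .95)

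*Combined protocol and SAP*

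**What the plan says.** Section 3.1 makes change in DQoL a primary endpoint, with baseline, 3 months and 6 months as its time frame. Section 5.3 confirms the visits: "Data were collected at three time points: baseline, 3 months, and 6 months". Section 5.2 places randomization after the baseline survey and adds: "Participants were randomized at a ratio of 1:1 using a random number generator".

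The analysis is in section 17.1, under Assessment of Intervention Effect; section 17.3 only refers back to it. The analysis variable is defined by "Change scores were calculated to determine differences between outcomes at baseline and 6 months". To judge whether changes in the intervention group were "significantly different than changes in the control group, t tests were used", two-tailed at .05. The analysis is by intention to treat, and on missing values the section says: "We imputed missing data using a Markov chain Monte Carlo method to conduct a five-fold multiple imputation". It names no baseline covariate, no variables for the imputation model and no pooling rule. Section 17.2 gives no power analysis.

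**The concern.** A t test on change subtracts the whole baseline score from the 6-month score, so it assumes that a one-point difference at baseline carries through as one point at 6 months. Where the true slope is lower, the subtraction adds baseline noise to the comparison. ANCOVA estimates the slope and removes only what baseline predicts.

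Baseline was measured before randomization, so it is a legitimate covariate, and it has already been collected. What is at stake is precision, not bias. With 48 randomized and no power analysis, precision is scarce. Chance imbalance also matters at this size: with 24 per arm (assumed), the standard error of the baseline difference is √(2/24) = 0.29 SD. At a slope of .5, an imbalance of one standard error moves the change-score estimate by 0.5 × 0.29 = 0.14 SD in that trial.

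Among the primary outcomes the point covers DQoL only, because section 17.1 names no analysis of the Cantril ladder.

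**Working it through.** **Inputs from the documents.** 48 randomized and 44 finished, with all four losses in the intervention arm (section 13.0); 1:1 allocation (5.2); two-sided .05, change scores, t tests and five imputations (17.1).

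**Assumptions, not in the documents.** Arms of 24 and 24; normal scores; correlation r between visits; k = 6-month SD ÷ baseline SD, equal to 1 unless stated; data missing at random. The plan states no power or sample-size figure to reproduce.

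**Variances.** Set the baseline SD to 1, so the slope is β = rk. Per person:

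- Change score: 1 + k² − 2rk, which equals k²(1 − r²) + (1 − β)².
- ANCOVA: k²(1 − r²) × [1 + 1/(N − 4)]; the bracket is the expected cost of estimating the slope.

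The change score thus carries an extra (1 − β)², which vanishes only at β = 1. The ANCOVA penalty is 1/44 = 2.3% at N = 48 and 1/40 = 2.5% at N = 44.

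**Equal SDs, no missing data, N = 48.** The ratio of ANCOVA to change-score variance is (1 + r)/2 × 1.0227. At r = .5 it is .75 × 1.0227 = .767. Simulation with 400,000 trials per setting gave .766, .869 and .971 at r = .5, .7 and .9. The ratios for other SD ratios come from the general formula:

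| k | r = .3 | r = .5 | r = .7 | r = .8 | r = .9 |
|---|---|---|---|---|---|
| 1 | .665 | .767 | .869 | .920 | .972 |
| 0.8 | .513 | .584 | .642 | .655 | .622 |
| 1.25 | .802 | .913 | 1.003 | 1.023 | .972 |

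At k = 1.25 and r = .8 the slope is exactly 1, so only the 2.3% penalty remains.

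**Half-width of the 95% interval at r = .5, k = 1.** Change: √(1 × 2/24) = 0.289, times 2.01 = 0.58 SD. ANCOVA: √(.75 × 1.0227 × 2/24) = 0.253, times 2.01 = 0.51 SD.

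**Break-even at k = 1.** Setting (1 + r)/2 × [1 + 1/(N − 4)] = 1 gives r = 2(N − 4)/(N − 3) − 1. This is 88/45 − 1 = .956 at N = 48 and 80/41 − 1 = .951 at N = 44.

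**Mixed respondents.** Caregivers answered for most participants, but "Participants with memory loss who did not have a caregiver completed surveys on their own behalf". A stable gap g between self-report and proxy scores, with a fraction p self-reporting, raises the correlation to r′ = (r + b)/(1 + b), where b = p(1 − p)g². With p = .2 and g = 1 SD (both assumed), b = .16. Then r = .3, .5, .7, .9 becomes .397, .569, .741, .914, and the ratios are .714, .802, .890, .979.

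**With five-fold imputation (modelled).** 20,000 trials per setting, with the four intervention participants missing both follow-up visits (assumed). Month 3 was imputed from arm and baseline, then month 6 from arm, baseline and month 3, and results were pooled by Rubin's rules with small-sample degrees of freedom. Each pair below is change score, then ANCOVA:

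| r | Variance ratio | Half-width, SD | Power, 0.6 SD effect | Power, 0.4 SD effect |
|---|---|---|---|---|
| .3 | .690 | .720, .602 | .368, .495 | .190, .250 |
| .5 | .795 | .613, .546 | .484, .577 | .247, .299 |
| .7 | .889 | .478, .451 | .688, .739 | .376, .417 |
| .9 | .978 | .278, .274 | .988, .990 | .805, .814 |

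At r = .5, .613/.546 = 1.12, so the change-score interval is 12% wider. Type I error was .048 to .050 for both methods.

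**The case against.** The strongest reply is that nothing here is wrong. The t test is unbiased under randomization, keeps its error rate and matches the endpoint as named. That stands in full. It does not defend the choice on precision, though: with baseline in the model, ANCOVA on change and ANCOVA on the 6-month score give the same arm effect, so adjusting leaves the endpoint as change.

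The second reply is that the size of the gain is unknown. This also stands: the documents give no r, no SD and no target effect, and the 0.4 and 0.6 SD effects are illustrations. The .95 threshold holds only for equal SDs. If the 6-month SD is 1.1 times the baseline SD, the change score is slightly better for r of about .82 to .95; at 1.25 times, for about .69 to .87. If the 6-month SD is 0.8 or 0.9 times baseline, ANCOVA is always better. The general condition is a slope near 1. What limits the objection is the asymmetry: the change score can win by about 2.5% in variance at most, while its loss can be many times that.

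Third, the imputation figures describe an assumed model. Section 17.1 does not give its variables or pooling rule, and section 13.0 does not say which visits were missed. They should be read as modelled, and the closed-form results without missing data point the same way.

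Finally, this is a completed pilot trial (sections 5.1 and 26.1), so the planned inference cannot now be changed. That restricts the remedy but does not remove the point.

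**Conclusion.** The concern holds as a matter of efficiency, with high confidence in the direction and much less in the size. If the SDs are equal, the loss is substantial at moderate correlation (about 23% of the variance at r = .5 with no missing data) and negligible at r = .9 (about 3%).

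The one hint in the documents is the DQoL alpha of .92 in section 17.1. If alpha is read as reliability and errors are independent over time, r could not exceed about .92. That is below break-even, but at that ceiling the ratio is .96 × 1.0227 = .98, a gain of only about 2%.

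The change is worth making because it is cheap and its downside is bounded. It is not a validity failure.

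A secondary point is that DQoL at 3 months is listed in section 3.1 and collected under section 5.3, yet section 17.1 specifies no arm comparison at that visit; its descriptive statistics name no visit.

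**What to change.** - In each of the five imputed data sets, fit ANCOVA of the 6-month DQoL score on arm and baseline score. Pool by Rubin's rules and report the adjusted difference with its 95% confidence interval beside the original t test, labelled post hoc.
- Report the baseline/6-month correlation and both SDs, so that readers can see whether the gain was material.
- State which variables the imputation model held. It should include arm and the baseline and 3-month scores. If arm was left out, re-impute: in the simulation, omitting it shrank a true 0.6 SD effect to .54 under both methods, so this matters whichever analysis is used.
- As a secondary step, report the same adjusted difference at 3 months, also labelled post hoc.
- In any further trial that reuses this plan, prespecify ANCOVA as the main analysis.

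The cost is one degree of freedom, about 2% in variance if the slope is near 1, and a few lines of code on data already collected. Re-imputation, if needed, adds more work.
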